5.4 Participant Withdrawal

Practitioners who contact network staff requesting withdrawal from further CORE Registry activities will be placed on a do not contact list and removed from study-related email communications.

5.4.1 Reasons for Participant Withdrawal

The NCC and NC staff will make reasonable efforts to determine reasons for study withdrawal and report results to the NCC and study team.

5.4.2 Handling of Participant Withdrawals

The study team and NCC staff will create and maintain a list of practitioners who request withdrawal from further CORE Registry study activities. These numbers will be included in recruitment results reporting.

It is anticipated that participants will not be replaced.

5.5 Premature Termination or Suspension of Study

This study may be suspended or prematurely terminated if there is sufficient reasonable cause. The SPI is responsible for promptly notifying all parties and providing the reason(s) for the termination or suspension.

Circumstances that may warrant termination include, but are not limited to:

- Insufficient adherence to protocol requirements.
- Data that are not sufficiently complete and/or evaluable.
- Determination of futility.

6. STUDY SCHEDULE

The CORE Registry study is conducted in five (5) phases over an approximate 12-month period.

6.1 Phase 1 – CORE Registry Questionnaire Wave 1 (CRQ1) and CRQ1 practitioner recruitment launch (T1 = Baseline + ~5 weeks)

- Recruit a target of approximately 38% of practicing dentists and hygienists over about 5 weeks to participate in Wave 1 of the CORE Registry study from a sample universe of all eligible U.S. dental practitioners enrolled in the National Dental PBRN.
- We expect enrollment to increase during the study period as new practitioners are continually recruited to the network, so the specific enrollment targets and target achievement will be defined at the time of CRQ1 launch.

6.2 Phase 2 – CRQ1 analysis and initial result dissemination

- CRQ1 responses are cleaned and analyzed by the CORE study team.
- Develop a CORE Registry Results Report Wave 1 (CRR1) and distribute to participating practitioners (CRQ1 respondents) through their individual Hub home pages. The CRR1 highlights initial CRQ1 summary statistics and CART analyses of SARS-CoV-2 transmission risks mitigation.
- Organize and deliver 3-5 CRR1 webinars (CRW1) for participating practitioners to disseminate and discuss CRR1 results and implications for practice. Webinar schedules will be developed in consultation with NCC and ARC staff. Webinar recruitment emails will be sent centrally by the NCC and regional NCs.
- Document receipt of CRR1 and attendance for 1≥ CRW1; provide CE for attendees.

6.3 Phase 3 – Conduct CORE Registry Questionnaire Wave 2 (CRQ2) (T2 = T1 + ~4 months (+~6-8 weeks))

- Conduct Wave 2 (CORE Registry Questionnaire Wave 2, CRQ2) with a target of 38% of U.S. dentists and hygienists enrolled in the Network at the time of Wave 2, over 6-8 weeks.
- Emphasize recruitment of CRQ1 respondents to maximize comparisons between Wave 1 and Wave 2 data.

6.4 Phase 4 - CRQ1 analysis and results dissemination for practitioners

- CRQ2 responses are cleaned and analyzed by the CORE study team
- Develop a CORE Registry Results Report Wave 2 (CRR2) and distribute to participating practitioners (CRQ2 respondents) through their individual Hub home pages. The CRR2 highlights initial CRQ2 summary statistics and CART analyses of SARS-CoV-2 transmission risks mitigation
- Organize and deliver 3-5 CRR2 webinars (CRW2) for participating practitioners to disseminate and discuss CRR2 results and implications for practice. Webinar recruitment emails will be sent centrally by the NCC and regional NCs.
- Document receipt of CRR2 and attendance for 1≥ CRW2; provide CE

6.5 Phase 5 – Study closeout and results reporting/dissemination

Complete analyses to address study objectives

7. STUDY PROCEDURES/EVALUATIONS

Questionnaire Development

The primary sources of information used to develop the Wave 1 survey include the CDC's interim and updated guidance for infection prevention and control for healthcare personnel, and guidance for dental facilities and staff, the American Dental Association Health Policy Institute recommendations and scientific webinars, OSHA guidelines, and the Organization for Safety, Asepsis, and Prevention (OSAP) in partnership with DentaQuest.

Drafts of the survey questions, responses, and content flow were developed by the study team and reviewed by NIDCR, the Data Committee, the Biostat Core, and Practitioner Executive Committee prior to finalizing the survey instrument. As part of the review process, the survey instrument was assessed to ensure it is psychometrically sound and to ensure the data collected will allow for adequate evaluation of study objectives.

The Wave 2 survey repeats survey items from Wave 1 and includes additional items to assess participant receipt of the Wave 1 Rapid Report, Wave 1 webinar attendance, and impacts of these activities on SC2 mitigation approaches and comfort levels. Depending on scientific development and guidelines related to SC2 transmission risks, some individual survey items or responses may be revised.

The Wave 2 survey will undergo the review process described above for the Wave 1 survey.

Questionnaire User Testing

The NCC will perform internal testing of the electronic study questionnaire and include testing internet browser compatibility. Study team members (e.g. PI, National Network Director, Node Directors, etc.) will be given the opportunity to externally test the website prior to administration to study participants.

Questionnaire Administration

Eligible participants will be identified from their responses to the network's enrollment questionnaire.

A waiver of documentation of signed informed consent for participants who complete the electronic questionnaire will be requested. Consistent with regulations outlined by the University of Alabama at Birmingham IRB and regional/local IRBs, information about the study will be provided to all eligible participants in the initial email invitation regarding the upcoming invitation to participate in the study. Completion of the questionnaire will indicate tacit consent.

After the initial invitation and 2 follow-up email reminders, the NCC will provide the NCs with a list of non-responders. The NCs will systematically contact non-responders to encourage questionnaire completion. If no feedback is received or the participant does

not complete the questionnaire after follow-up attempts over a period of up to three months, it will be assumed the practitioner is not interested in the study.

Cognitive Interviewing

Cognitive testing of the survey instrument was completed, in which dentists reviewed their responses to a completed survey and were probed to assess possible respondent problems in understanding questions, recalling necessary information, and/or reporting information accurately.

Questionnaire Testing-Retesting

User testing may also include test-retests of survey questions by survey participants. Test-retest may be performed for the Wave 2 questionnaire if warranted after analyses of Wave 1 results.

8. ASSESSMENT OF SAFETY

8.1 Definitions of Safety Parameters

.

8.1.1 Unanticipated Problems

The Office for Human Research Protections (OHRP) considers unanticipated problems involving risks to subjects or others to include, in general, any incident, experience, or outcome that meets all of the following criteria:

- unexpected in terms of nature, severity, or frequency given (a) the research procedures that are described in the protocol-related documents, such as the IRB-approved research protocol and informed consent document; and (b) the characteristics of the subject population being studied;
- related or possibly related to participation in the research (possibly related means there is a reasonable possibility that the incident, experience, or outcome may have been caused by the procedures involved in the research); and
- suggests that the research places subjects or others at a greater risk of harm (including physical, psychological, economic, or social harm) than was previously known or recognized.

8.2 Specification of Safety Parameters

Safety monitoring for this study will focus on unanticipated problems involving risks to participants.

8.3 Reporting Procedures

8.3.1 Unanticipated Problem Reporting

Per National Dental PBRN procedures, unanticipated incidents and events will be reported to the PI. After the PI is made aware of the incident/event, the following procedures will be followed.

Incidents or events that meet the OHRP criteria for unanticipated problems require the creation and completion of an unanticipated problem report form. OHRP recommends that investigators include the following information when reporting an adverse event, or any other incident, experience, or outcome as an unanticipated problem to the IRB:

- appropriate identifying information for the research protocol, such as the title, investigator's name, and the IRB project number;
- a detailed description of the adverse event, incident, experience, or outcome;

- an explanation of the basis for determining that the adverse event, incident, experience, or outcome represents an unanticipated problem;
- a description of any changes to the protocol or other corrective actions that have been taken or are proposed in response to the unanticipated problem.

To satisfy the requirement for prompt reporting, unanticipated problems will be reported using the following timeline:

- Unanticipated problems will be reported to the IRB as soon as possible but in all cases within 10 working days of the investigator becoming aware of the problem.
- All unanticipated problems should be reported to appropriate institutional officials (as required by an institution's written reporting procedures), the supporting agency head (or designee), and OHRP within one month of the IRB's receipt of the report of the problem from the investigator.

All unanticipated problems will be reported to NIDCR concurrently with reporting to the IRB. These reports will be made to NIDCR's centralized reporting system via the Clinical Research Operations and Management Support (CROMS) contractor.

- Product Safety Fax Line (US): [name]
- Product Safety Fax Line (International): [contact]
- Product Safety Email: [contact]

9. STUDY OVERSIGHT

The PI will be responsible for study oversight, including monitoring safety, ensuring that the study is conducted according to the protocol and ensuring data integrity. The NCC will provide the PI with current data summaries, and the PI will review the data for safety concerns and data trends at regular intervals, and will promptly submit reportable events to the IRB and NIDCR that arise during the conduct of the study, per the IRB's reporting time-frame requirements. To ensure data integrity, the PI, NCC, and study team will adhere to data quality management processes (please see Section 13).

10. CLINICAL SITE MONITORING

No outside clinical site monitoring will be employed for this study. The NCC is responsible for launching the study and collecting data received as part of the study. Quality Assurance/Quality Control activities associated with data collection and processing will be developed by the NCC. The NCC will ensure that the quality and integrity of the study data and data collection are maintained. The NIDCR reserves the right to conduct independent clinical site monitoring as necessary.

11. STATISTICAL CONSIDERATIONS

11.1 Study Hypotheses

This is an observational study that has both cross-sectional and longitudinal components. The study objectives do not include testing specific hypotheses, but rather identifying groups of practitioners using recommended approach to mitigate coronavirus transmission risks in dental offices.

Sample Size Considerations

For the CORE Registry study, we seek to enroll about 38% of eligible U.S. practitioners in the National Dental PBRN, which includes a target of about 45% of underrepresented minority practitioners in the network.

Sample size and power for primary outcome. The primary objective is to identify mutually exclusive combinations of approaches practitioners use to mitigate SARS-CoV-2 transmission risks at dental offices, and practitioner characteristics associated with differences between these combinations of approaches.

A recruitment and analysis plan has been developed that provides 80% power to detect significant differences between groups, assuming a two-tailed alpha level of .05 and accounting for intraclass correlations. It is expected that a large (about 2,000) and diverse sample of Network practitioners will participate in the study. In addition, use of CART modeling will enable evaluation of subgroups of variables with as few as 10-15 observations.(17,18) There are a limited number of covariates in the analysis plans, such as practice location (region/state), practice setting (solo, large group, academic, community/public health), practice type (general dentist, dental specialty, dental hygienist, dental therapist), and practitioner characteristics (years since dental school graduation, race-ethnicity, gender, etc.). Sub-group comparisons of some URM participants will be challenging given the current enrollment in the network.

Recruitment for the Wave 2 questionnaire (CRQ2) will be focused on practitioners who participated in Wave 1 (CRQ1) to support analyses of differences.

11.2 Final Analysis Plan

Two surveys of National Dental PBRN practitioners will be conducted to identify the approaches that practitioners and practices use to mitigate the risks of SC2 transmission for patients and dental office staff. The two surveys also collect information about sources of information and guidelines relevant to coronavirus risks and risk mitigation, practitioner-reported expenditures for mitigation (one time and recurring and monthly expenditures), weekly work hours and patient volume, and comfort or confidence levels with risk mitigation approaches and safe practice recommendations.

Participants and data.

In addition to survey data, the study team collects information on relevant practice guidelines and epidemiologic data from national and state sources, and practitioner information from the National Dental PBRN Enrollment Questionnaire (EQ).

EQ data includes practice location (region/state/county), practice setting (solo, large group, academic, community/public health), practice type (general dentist, dental specialty, dental hygienist, dental therapist), and practitioner characteristics (age, years since dental school graduation, race-ethnicity, gender, etc.).

Study measures. For this study, we separate SC2 transmission risks for dental care into four types (pathways): patient-to-staff (P2S); patient-to-patient (P2P); staff-to-patient (S2P); and staff-to-staff (S2S). Different risk mitigation approaches may address one or more pathway, but not every approach can address each pathway. We also group SC2 risk mitigation approaches into one of four categories (or types): practice facility and equipment (FAC); practitioner and staff (STAFF); Office Visits (VISIT) including patient flow and dental procedures; and personal protective equipment (PPE).

Practice-level (FAC) modifications include facility and equipment changes, patient flow redesign, and surface disinfectant procedures. Practitioner and staff (STAFF) modifications include workforce changes in hours worked and patient volume, and personnel measures to reduce or manage coronavirus exposure. Office visit (VISIT) modifications include changes to patient screening for COVID-19 and changes to aerosol generating dental procedures and techniques used. We also collect information on PPE use during dental and dental hygiene procedures, and access to PPE supplies.

We use published information obtained from the CDC, ADA, OSHA, and other sources to assign each approach to a pathway and category, noting that individual approaches may apply to more than one transmission pathway.

The primary outcome measure is individual and grouped practitioner-reported mitigation approaches. There are four secondary outcome measures: 1) total and monthly expenditures for mitigation; 2) level of comfort/confidence with guidelines and mitigation approaches used; 3) changes in mitigation approach, costs, and comfort/confidence between Wave 1 and Wave 2 questionnaires; and 4) successful integration of a COVID-related X01 study.

Addressing study Objectives. Objective 1 (Primary). Identify and compare the use of recommended approaches among National Dental PBRN practitioners to mitigate SARS-CoV-2 transmission risks at dental offices, by transmission pathway and mitigation type.

We will use data from the two surveys to identify distinct combinations of risk mitigation approaches, by type and transmission pathway, used by National Dental PBRN practitioners, overall and for different practitioner subgroups. First, we will examine the frequencies of individual approaches by type and pathway, that are reported by distinct groups of practitioners. We will use these results to inform a process to combine approaches within each type and pathway among subgroups of practitioners.

For the Wave 1 questionnaire, mitigation approaches reported by participating practitioners are grouped by approach type and transmission pathway. For each type and pathway, responses to individual approach questions are classified as either dichotomous (yes/no) or ordered by frequency of performance on a 5-point Likert scale. While responses to each approach will be examined individually, we expect to grade responses as "following practice guidelines" for an individual recommended approach that has a "yes" or "always" response. If warranted, we will also consider adding the "almost always" as a following practice guidelines response. The outcome measure analyses are represented by the following individual and group level assessment of mitigation approaches:

Ind: Approach i,p,t, = f(practice setting, practice type, practice location, guideline source and last review, practitioner demographics, COVID history, mitigation costs, work hours, patient volume)

Grouped: Rec Approach _{i,p,t}, = f(practice setting, practice type, practice location, guideline source and last review, practitioner demographics, COVID-19 history, mitigation costs, work hours, patient volume)

where i = individual approach, p = pathway, and t=approach type; and Rec Approach is a dichotomous (yes/no) variable for each approach recommended approach that is followed, indicated as "yes" or "always", by type and pathway. A yes to all recommendations receives a score of "1" and all other combinations receive a "0."

First, we will examine the frequencies of individual approaches by type and pathway, that are reported by distinct groups of practitioners. We use these results to inform a process to combine approaches within each type and pathway among subgroups of practitioners. We will use CART analyses to identify distinct and mutually exclusive groups of practitioners using common sets of recommended mitigation approaches.

The grouped level analysis is speculative. We will compare the correspondence with the group-level model results with individual-level model results using appropriate statistical methods.

Objective 1 (secondary). Estimate mean total fixed and monthly expenditures to mitigate SARS-CoV-2 transmission risk, overall and for mutually exclusive groups of practitioners identified by the primary objective analysis

We will estimate mean reported total and monthly recurring expenditures and 95% confidence intervals for SC2 mitigation approaches, overall and by type (FAC, STAFF, VISIT, PPE) and pathway (P2S, S2P, S2S, P2P). We will then evaluate mean expenditures and CIs for groups of practitioners identified in Objective 1.

Objective 2 (secondary): Assess mean levels of comfort and/or confidence with available information and guidelines for infection control, approaches used to mitigate SARS-CoV-2 transmission risks, and the financial impact of mitigation, overall and for mutually exclusive groups of practitioners identified by the primary and secondary objective analyses.

We use 5-point Likert scales to estimate practitioners' mean comfort and/or confidence levels for select mitigation guidelines, type, and pathway. We estimate mean comfort levels for each group of practitioners identified in the Objective 1 analysis.

Objective 3 (secondary): Disseminate the Wave 1 Rapid Report and conduct informational Rapid Report Webinars with network practitioners, and assess the impacts of Report dissemination on changes in practitioners' mitigation approaches, mitigation costs, and comfort levels, overall and for different practitioner subgroups

Changes in virus mitigation approaches will be assessed by comparing Wave 2 with Wave 1 data for practitioners who complete both surveys. Wave 2 survey includes questions for assessing the impact of Rapid Reports and webinars from Wave 1 on practitioner decision making.

Changes in comfort levels will also be assessed, which is relevant for respondents who may not change their mitigation approach but may have improved confidence in the approaches they use. These would otherwise go unmeasured. We will use CART analysis to separately identify mutually exclusive groups of practitioners with common overall levels of comfort with their existing risk mitigation approaches from Questionnaires 1 and 2, and practitioners who report changes in comfort levels between the two surveys.

Objective 4 (secondary): Establish a modular infrastructure to support the design and conduct of additional multilevel clinical and implementation science research.

We are enabling additional modules to be incorporated into the CORE Registry through NCC participation with newly funded study teams who are addressing COVID-related research topics. This will involve developing common measures, integrating study data into the Registry structure, and other activities as necessary given available resources. The survey date will support numerous additional analyses, which will be developed as time and resources allow.

The objective 4 outcome will be measured as the successful integration of one or more additional COVID-related network study. Capability for expansion is designed into the

Registry as the CORE Registry study modules are built.

Missing data. Data from incomplete questionnaires may be included in data analyses. Depending on the extent of missing data and available resources for analyses, the study team may consider statistically appropriate methods for imputing missing information.

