5. STUDY POPULATION

We plan to recruit a target of approximately 38 percent of all active U.S dental practitioners (dentists, dental hygienists and dental therapists) who are enrolled in the National Dental PBRN at the time of recruitment. There are currently about 5300 active U.S. practitioners who are eligible to participate.

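### With state (about 50 levels) admitted as a CART covariate, chance splits on state can displace real differences below about 12 to 15 points

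*Protocol*

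**What the plan says.** Section 4 (Study Design) names location, with practitioner type and practice setting, among the factors that CART will assess. Section 11.1 gives its coding: "There are a limited number of covariates in the analysis plans, such as practice location (region/state". The closing bracket follows state, so region and state are the two levels named. In section 11.2 practice location enters the individual and the grouped model for the primary objective without a level: "f(practice setting, practice type, practice location, guideline source and last review, practitioner demographics". The same section assigns the tree its task: "We will use CART analyses to identify distinct and mutually exclusive groups of practitioners using common sets of recommended mitigation approaches".

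The list of Enrollment Questionnaire data in section 11.2 is finer: "EQ data includes practice location (region/state/county), practice setting (solo, large group, academic, community/public health". That sentence describes what is held, not what is offered to the tree.

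Section 2.2 says that all states are represented in the network. On sample size, section 5 says "There are currently about 5300 active U.S. practitioners who are eligible to participate", and section 11.1 says "we seek to enroll about 38% of eligible U.S. practitioners in the National Dental PBRN" and "It is expected that a large (about 2,000) and diverse sample of Network practitioners will participate in the study". Section 11.1 also expects CART to work with subgroups of 10 to 15 observations. The protocol gives no split-selection rule, pruning rule or loss function.

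**The concern.** Standard CART tries every two-way grouping of a categorical predictor and keeps the best. A four-level practice setting offers 2^3 − 1 = 7 groupings; a 50-level state factor offers 2^49 − 1. The best of so many looks strong even when state has nothing to do with the outcome. Section 11.1 calls the covariates limited, which is true of the number of variables but not of the number of levels.

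The primary objective is to find groups of practitioners and the characteristics that distinguish them. If the first split is a chance list of states, the later groups are built inside it. Secondary objectives 1 and 2 then report costs and comfort by those groups, and section 6.2 puts Wave 1 CART results into the report sent to respondents before Wave 2.

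**Working it through.** **Inputs from the protocol.** Eligible practitioners 5,300 and target 38% (sections 5 and 11.1); expected respondents about 2,000 (11.1); about 50 states (2.2); location as region/state (11.1); small subgroups of 10 to 15 (11.1; 15 taken as minimum node).

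**Assumptions.** Outcome rate 50% (30% as a sensitivity case), independent respondents, no true state effect, and in the main calculation one real predictor split 50/50.

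**1. The plan's own figure.** 0.38 × 5,300 = 2,014, which agrees with about 2,000. Per state: 2,000 / 50 = 40 on average.

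**2. A scale for comparison.** For two groups of 1,000 at a 50% rate, the standard error of a difference is √(0.25 × 2/1,000) = 0.02236, so chi-square ≈ 2,000 × d². The difference with 80% power at two-sided 0.05 is (1.96 + 0.84) × 0.02236 ≈ 0.0625, or 6.25 points (chi-square 7.8). This is only a yardstick: section 11.1 gives no effect size, base rate or intraclass correlation, so its power statement cannot be reproduced.

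**3. What a noise state factor produces.** Cutting 50 states of 40 at the median observed rate gives an expected gap of 2 × 0.798 × √(0.25/40) = 0.126. Simulating the full search (1,000 datasets) gives a mean best-split chi-square of 32.0 (5th to 95th percentile 21.7 to 44.4), and 29.1 with unequal states. As differences these are √(32.0/2,000) = 12.6 points and √(29.1/2,000) = 12.1 points. A seven-level region factor gives 4.6, or √(4.6/2,000) = 4.8 points.

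**4. Who takes the first split.** Hand check at 10 points: the real predictor's chi-square has mean 20 + 1 = 21 and variance 2 × (1 + 2 × 20) = 82. State has mean 32.0 and SD (44.4 − 21.7)/3.29 = 6.9. Then P(state wins) ≈ Φ((32 − 21)/√(82 + 47.6)) = Φ(0.97) ≈ 0.83. Simulation agrees:

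| True difference (points) | Noise state beats the real predictor |
|---|---|
| 6.25 | 99% |
| 10 | 83% |
| 12.5 | 50% |
| 15 | 17% |
| 20 | 0.2% |

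Simulations at N = 2,014, with the real 10-point effect placed on practice setting, give 74% and 78%. Region in place of state wins in about 2% of datasets or less. At a 30% outcome rate, a real 10-point predictor takes the root in only 25% of datasets with equal states and 30% with unequal states.

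**5. After the first split, under assumed pruning rules.** Share of 400 trees that keep the real predictor after 10-fold cross-validated pruning on squared error (minimum-error tree, 50% rate):

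| True difference (points) | Without state | With state |
|---|---|---|
| 6.25 | 27% | 0% |
| 10 | 78% | 4% |
| 12.5 | 96% | 21% |
| 15 | 99% | 57% |
| 20 | 100% | 99% |

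With misclassification loss at 10 points, the real predictor is kept in 76% of trees with state (97% without), but the noise state split is also kept in 82%. The form of the harm therefore depends on the rule.

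**6. Does another tree method help?** If variables are ranked by p-value before any split search, a noise state factor has a uniform p-value. A real 10-point predictor has z centred on √20 = 4.47, so state wins with probability about 2 × Φ(−4.47/√2) = 2 × Φ(−3.16) ≈ 0.0016. Simulation also ranks the real effect first in over 99% of datasets.

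**The case against.** Four objections carry weight.

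- **County.** A reader might infer from the data inventory in section 11.2 that county is a candidate split. The document does not say so: the covariate list stops at state, and no other place offers county to the tree. The point is therefore confined to state.
- **Pruning.** A reader might conclude that the plan's pruning will delete real findings. No pruning is described, so step 5 shows possible consequences, not the plan's own. A split rule without this bias is not excluded either.
- **State may matter.** Sections 2.1, 3.1 and 12 describe state-level reopening decisions, recommendations, regulations and incidence. A state split could be genuine, and simply deleting state could lose information. This stands and shapes the fix. But chance alone reaches 12 to 13 points, so a state split cannot by itself show which it is.
- **Level of detail.** Coding and tuning may be settled in an analysis plan or in the standard operating procedure mentioned in section 15.3, and region is already one of the two named levels. That would answer a complaint about silence. Here, though, section 11.1 itself names state as a covariate alongside CART.

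It is also tempting to say that this contradicts the claim that the plan "provides 80% power to detect significant differences between groups, assuming a two-tailed alpha level of .05 and accounting for intraclass correlations". The text does not tie that claim to a CART split: CART is introduced separately afterwards, and section 11.1 disclaims specific hypotheses. The frequency tables planned in section 11.2 could also reveal a difference that the tree misses.

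**Conclusion.** The point holds for state. If state enters a standard exhaustive-search CART with about 2,000 respondents, a state factor with no real effect competes like a 12- to 13-point difference. It takes the first split from a real 10-point difference in about 74 to 83% of datasets at a 50% outcome rate, against about 2% or less for region. Real differences below about 12 to 15 points can be masked or displaced; differences near 20 points survive. The figures assume independent respondents and no true state effect. The first-split result needs no assumption about pruning; whether the real predictor is then lost, or kept beside a spurious state split, does depend on the unstated rule. The protocol does not support the stronger readings that county is a candidate split, that pruning will remove real findings, or that every state split is chance.

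**What to change.** State in sections 11.1 and 11.2 which level of location enters the trees, before the Wave 1 analysis, using one of two options:

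- **State stays a candidate split.** Grow the trees with a method that separates variable selection from split search, such as a conditional inference tree or GUIDE. The cost is a different tree routine and a slightly more conservative tree; state information is retained.
- **State is left out of the trees.** Enter location as network region (six regional nodes plus the specialty node) together with the state and local incidence and regulation measures already collected under section 12, and tabulate results by state separately. A numeric measure with one value per state offers at most 49 ordered cuts instead of 2^49 − 1 groupings. The cost is that the tree cannot directly isolate a single outlying state, which the separate table would show.

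Either option takes a sentence or two and needs no new data. The first is preferable if real state differences are of interest, because it does not discard them.
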